6.3 ADDITION OF AZACITIDINE FOR NON-RESPONSE

If at end of two cycles of tosedostat, patient does not have response as defined as above, the investigator has discretion of adding azacitidine in addition to tosedostat. Dosing will be standard dosing (azacitidine 75mg/m²), either subcutaneously or intravenously, for 5 continuous days every 28 days.

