8 STATISTICS

This is an open-label, phase II study designed to explore the clinical activity of tosedostat in patients with MDS who have failed therapy with hypomethylating agents. The study will include 80 patients with high and very high risk MDS with the goal of doubling median overall survival from 6 to 12 months. A futility analysis will be performed after the first 40 patients are treated, and if the median overall survival is less than 3 months, then we will consider closing the study.

Sample size considerations:

The primary endpoint for is overall survival, as measured from the start of the treatment to the date of death (or date of last follow-up if no death). Previous data suggest that the median overall survival for high risk MDS patients is 6.0 months. With the administration of tosedostat, we anticipate the median overall survival to be improved to ≥ 9 months. A sample size of 80 patients is planned for this study, which will give us at least 85% power to detect the hypothesized improvement. This calculation assumes a Type I error of 10%, a one-sided test, and a median follow-up time of 2.5 years. It also assumes that survival times are exponentially distributed. This last assumption is for planning purposes only; actual analysis will employ nonparametric methods for estimation and testing of survival distributions. A two-sided 95% confidence interval for the median overall survival is estimated to be (6.2 months, 12.7 months) under the hypothesized improvement. At an accrual rate of 3-4 patients per month, we anticipate to complete enrollment in approximately two years.

Analysis Plan:

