The median overall survival will be estimated by the Kaplan-Meier method and 95% confidence intervals for overall survival estimates will be calculated using Greenwood's formula. Descriptive statistics will be utilized to describe the parameter proportions defined above (i.e., frequency, percent). Estimated differences in the transfusion independence proportion/overall survival between categories of demographic and treatment variables (evaluated by the two-sample t-test, Wilcoxon rank-sum test, Fisher's exact test, and log-rank test, as appropriate) will serve as preliminary data (i.e., hypothesis-generating) for future studies. All p-values will be two-sided with statistical significance evaluated at the 0.05 alpha level. Ninety-five percent confidence intervals will be calculated to assess the precision of the obtained estimates. All analyses will be performed in SAS Version 9.4 (SAS Institute, Inc., Cary, NC) and Stata Version 14.0 (StataCorp, College Station, TX).

Safety Analyses

Safety analysis will include AE summary tables using Medical Dictionary for Regulatory Activities (MedDRA) and NCI CTCAE criteria, changes in physical examination and performance status, ECG, and laboratory summary tables and figures.

Adverse Events

Adverse events occurring during the AE reporting period (see Section 7.3) will be summarized. They will be tabulated by SOC and by preferred term within SOC according to MedDRA. Severity will be graded using the NCI CTCAE. While the goal is to collect 28-day follow-up data, it is possible that patients may proceed to other anticancer therapies before completing the 28-day follow-up.

Exact 95% confidence intervals around the adverse event proportions will be calculated to assess the precision of the obtained estimates.

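### Overall survival is to be compared by unlisted treatment variables with a log-rank test from treatment start; if azacitidine added after cycle 2 is one of them, the comparison carries immortal time

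*Combined protocol and SAP*

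**What the plan says.** Section 8, Sample size considerations, defines overall survival "as measured from the start of the treatment to the date of death". The Analysis Plan in the same section then compares overall survival "between categories of demographic and treatment variables". It lists four tests to be used as appropriate, of which only the log-rank test is for survival data. Significance is two-sided at 0.05, and the results are described as hypothesis-generating input for later studies. The section does not list the treatment variables, and it names no landmark, time-dependent covariate or other handling of treatment begun after time zero.

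All patients start tosedostat at the same dose (Sections 3.1 and 6.2). Under Section 6.3, for a patient without response at the end of two cycles, "the investigator has discretion of adding azacitidine in addition to tosedostat". Section 3.2 describes the group more narrowly, as stable disease without hematological improvement. Section 5.7.4 requires tosedostat to stop on disease progression. A cycle is 28 days (Section 5).

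**The concern.** In a single-arm trial with one starting dose, azacitidine is the main treatment category that differs on study, and Section 3.2 gives a scientific reason to look at it (possible synergy or restored sensitivity). To be counted as an azacitidine patient, one must first survive about 56 days. Those days are credited to the azacitidine group although no death in that group could occur in them, and all early deaths are charged to the other group. An add-on with no effect can then appear to lengthen survival. These comparisons are meant to inform future studies, and a combination trial is an obvious candidate. Calling them hypothesis-generating tempers the inference but does not remove a directional bias.

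**Working it through.** **Inputs from the documents.** N = 80 (Section 8). "Previous data suggest that the median overall survival for high risk MDS patients is 6.0 months"; with tosedostat, "we anticipate the median overall survival to be improved to ≥ 9 months". "It also assumes that survival times are exponentially distributed". "This calculation assumes a Type I error of 10%, a one-sided test, and a median follow-up time of 2.5 years". Two cycles = 56 days = 56/30.4375 = 1.84 months.

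**Inputs assumed.** The share of day-56 survivors who receive azacitidine is not in the documents; 25%, 50% and 75% are used. Response and progression shares, and the hazards that go with them, are also assumptions. Azacitidine is given no effect throughout.

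**The plan's own figure.** The plan states: "A sample size of 80 patients is planned for this study, which will give us at least 85% power to detect the hypothesized improvement". A one-sample test of 6-month survival reproduces this. The null is 0.50 and the alternative is 0.5^(6/9) = 0.630. Power = Φ{[0.130 − 1.2816·√(0.25/80)] / √(0.630·0.370/80)} = Φ(1.08) = 86.0%. The planning model is therefore read as intended. The documents give no figure for the comparison at issue.

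**Step 1: deaths before azacitidine is possible.** The proportion is 1 − 0.5^(1.84/median).
- Median 6 months: 1 − 0.5^(0.307) = 19.1%.
- Median 9 months: 1 − 0.5^(0.204) = 13.2%.

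**Step 2: immortal time alone.** Simulated trials of 80 patients, exponential survival, 30 months of follow-up, and an inert add-on at day 56 given at random to survivors. Ever versus never azacitidine is compared by log-rank from treatment start, with z = (O − E)/√V, a false benefit if z < −1.96, and apparent hazard ratio exp[(O − E)/V].

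| Median | Share of survivors treated | Apparent HR | False benefit |
|---|---|---|---|
| 6 months | 25% | 0.80 | 10.7% |
| 6 months | 50% | 0.69 | 34.3% |
| 6 months | 75% | 0.47 | 72.9% |
| 9 months | 25% | 0.85 | 8.1% |
| 9 months | 50% | 0.76 | 21.5% |
| 9 months | 75% | 0.56 | 51.5% |

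At 50% uptake the apparent medians are 7.9 v 4.5 months (true median 6) and 11.0 v 7.5 months (true median 9). A separate run with follow-up uniform on 18-42 months rejects in 35% and 21% at 50% uptake. Under the same random assignment, a day-56 landmark test and a time-dependent log-rank test reject in 4.1-6.2% of trials, close to the nominal 5%.

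**Step 3: selection as the protocol has it.** Responders and progressors are not given azacitidine.
- Responders 10-30% and progressors 10-30% of survivors, hazards 1.5-2 fold better or worse than stable disease, 50% uptake in the rest: the plain log-rank HR is 0.72-0.99, with false benefit in 1.5-24% of trials.
- Responders the only excluded group, numerous (20-50%) and much longer-lived: the HR can reach or pass 1, up to 1.59.
- Progressors the only excluded group, 30% at doubled hazard, median 6 months, 50% uptake: false benefit in about 51%.

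**Step 4: whether a simple landmark is enough.** Median 6 months, 50-75% uptake among those eligible, inert add-on.

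| Excluded group | Plain log-rank | Landmark, all alive | Landmark, eligible only |
|---|---|---|---|
| 30% responders at half the hazard | false benefit 2-4% | false harm 23-40% | rejects about 5-7% |
| 30% progressors at doubled hazard | false benefit about 51% at 50% uptake | false benefit 15-33% | rejects about 5-7% |

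A landmark among everyone still alive removes the immortal time but leaves the selection. Restricting it to patients who could have been given azacitidine at that assessment restores approximately the nominal level in these settings.

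**The case against.** The strongest reply is that this comparison is inferred. Azacitidine is not named as a treatment variable, and prior treatment fits the phrase at least as well: Section 4.1 distinguishes decitabine from azacitidine and refractory from relapsed and intolerant patients, and Section 5.1 records previous regimens. A plain log-rank test is sound for those variables. This stands. A reader might infer that Section 8 commits the trial to a biased test; it does not go that far. The phrase on choosing tests as appropriate leaves room for judgement, although none of the four listed tests handles a treatment that starts after time zero.

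A reader might also infer that an inert add-on would necessarily look beneficial. The documents do not support that either. Azacitidine goes to non-responders, which pushes against it, and progressors must stop, which pushes for it. Step 3 shows that the net size, and in some settings the direction, is not settled. What remains is that immortal time always acts in azacitidine's favour, and a second bias of unknown direction is no reason to leave it in.

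Finally, the comparison is exploratory. That limits its importance but does not make it harmless, given its stated use.

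**Conclusion.** The point holds in a conditional form. If overall survival is compared by azacitidine with the test that Section 8 names, deaths before about day 56 (19.1% or 13.2% of patients at medians of 6 or 9 months) can fall only in the no-azacitidine group. With random uptake of 50% among survivors, immortal time alone gives a false benefit in about 35% or 21% of trials. These figures rest on exponential survival and an assumed uptake; at 25% uptake they fall to 8-11%, still above the nominal 2.5% in that direction. Under response-based selection the net result may be larger, smaller or reversed. The mechanism is certain; the net magnitude and direction are not.

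It would be wrong to read this as a flaw in the primary analysis. The Kaplan-Meier median, the sample size and the futility rule do not use this comparison.

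**What to change.** In the Analysis Plan of Section 8:

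1. List the treatment variables, and keep the plain log-rank test for those known at treatment start (demographics, prior hypomethylating therapy).
2. For azacitidine, start the clock at the end-of-cycle-2 response assessment. Include only patients then alive, still on tosedostat, and without response or progression, and class them by whether azacitidine is added at that assessment. Alternatively, use a time-dependent covariate from the actual azacitidine start date within the same eligible group. Anchoring on the assessment or start date is safer than a fixed day 56, since interruptions of up to 14 days (Section 3.1) and the ±10-day marrow window (Appendix 1) can move it.
3. Treat other post-baseline variables (dose reduction, response) as time-dependent. A single cycle-2 landmark does not suit response, which may occur up to cycle 4 (Section 4.3).
4. State that these comparisons remain non-randomised.

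Sections 3.2 and 6.3 describe the azacitidine group differently and should be reconciled so that the analysis group is unambiguous.

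The cost is one or two sentences and fewer patients in this exploratory comparison. Sample size, conduct and the primary analysis are unchanged.

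### Overall survival is sized on a one-sided 10% test, but the Analysis Plan puts all p-values at two-sided 5% and names no test or success rule against 6.0 months

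*Combined protocol and SAP*

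**What the plan says.** **Section 8, Sample size considerations.** The primary endpoint is overall survival (OS) from start of treatment. The reference value is historical: "Previous data suggest that the median overall survival for high risk MDS patients is 6.0 months". The planning alternative is a median of 9 months or more. Eighty patients are planned, "which will give us at least 85% power to detect the hypothesized improvement". The level is explicit: "This calculation assumes a Type I error of 10%, a one-sided test, and a median follow-up time of 2.5 years". Exponential survival is assumed for the calculation only, and "actual analysis will employ nonparametric methods for estimation and testing of survival distributions". The section adds an expected precision: "A two-sided 95% confidence interval for the median overall survival is estimated to be (6.2 months, 12.7 months) under the hypothesized improvement".

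**Section 8, Analysis Plan.** For OS this gives a Kaplan-Meier median with 95% confidence intervals. The only tests named are for comparisons between categories of patients, "evaluated by the two-sample t-test, Wilcoxon rank-sum test, Fisher's exact test, and log-rank test, as appropriate", and these are labelled hypothesis-generating. The next sentence reads "All p-values will be two-sided with statistical significance evaluated at the 0.05 alpha level".

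**Elsewhere.** The only numerical decision rule on OS is the interim futility rule (median below 3 months after 40 patients, Sections 7.4.4 and 8). The move from 6 to 12 months in Sections 3.2 and 8 is stated as a goal or endpoint, without a test or threshold attached.

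**The concern.** The sample size paragraph promises a hypothesis test of the primary endpoint and attaches a power to it. The Analysis Plan contains no such test, and its one statement about significance levels, taken as written, sets a different level and a different sidedness. A result with a one-sided p-value between 0.025 and 0.10 is positive under the first paragraph and negative under the second.

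This matters more here than in a randomised trial. The study is single-arm and open-label, so the comparison with a fixed 6.0 months is the whole of the primary inference. If the rule is not fixed in advance, the choice between the two levels, and the choice of test, can be made after the data are seen.

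**Working it through.** **Inputs (Section 8).** n = 80; reference median 6.0 months; alternative 9 months; exponential survival for planning; one-sided 10% (z = 1.2816) against two-sided 5% (z = 1.9600 in the favourable direction).

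**1. Reproduce the stated power.** The section calls for nonparametric testing, so take the test of median 6.0 months as a test of 6-month survival, S(6) = 0.50. Under a 9-month median, S(6) = 2^(−6/9) = 0.630.

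Power = Φ[(0.130 − z·√(0.25/80)) / √(0.63·0.37/80)] = Φ[(0.130 − 0.0559z)/0.0540]

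- z = 1.2816: 86.0%, which agrees with at least 85%.
- z = 1.9600: 64.7%.

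Converting exactly 85% from one level to the other gives Φ(1.0364 + 1.2816 − 1.9600) = Φ(0.358) = 64.0%.

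**2. Check that the planning was nonparametric.** Inverting the same test at a 9-month median gives survival limits 0.5 ± 1.96·0.0559 = 0.610 and 0.390, hence times −9·log₂(0.610) = 6.4 and −9·log₂(0.390) = 12.2 months. A parametric exponential interval with 80·(1 − 2^(−30/9)) = 72 events would be 9·exp(±1.96/√72) = 7.1 to 11.3. The protocol's 6.2 to 12.7 resembles the first, not the second. Its expected lower 95% limit lies only 0.2 months above 6.0, which is itself hard to square with 85% power at two-sided 5%.

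**3. Sample size for 85% power on this test.** n = [(0.5z + 1.0364·0.4828)/0.130]²

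- One-sided 10%: 77.1, so 78 patients, close to the planned 80.
- Two-sided 5%: 129.8, so 130 patients.

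**4. Dependence on the unnamed test.** Power at a 9-month median:

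| Test against 6.0 months | One-sided 10% | Two-sided 5% |
|---|---|---|
| 6-month survival, normal approximation | 86.0% | 64.7% |
| 6-month survival, exact binomial | 81.7% | 58.6% |
| Lower Kaplan-Meier limit for the median above 6.0 | 86.9% | 67.1% (plain), 58.2% (log-log) |
| One-sample log-rank, exponential reference | 98.0% | 92.7% |

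The last two rows are simulated: 10,000 trials, exponential survival, uniform accrual over 24 months, and an assumed cut-off at month 42. Potential follow-up then runs from 18 to 42 months with median 30, matching the 2.5 years in the protocol. Monte Carlo standard error is at most √(0.25/10,000) = 0.5 points.

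**5. Results that change sign.** With the exact binomial test, one-sided 10% rejects at 47 or more of 80 alive at 6 months, and two-sided 5% at 50 or more (one-sided p = 0.0165).

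- 47, 48 or 49 alive give one-sided p of 0.073, 0.046 and 0.028: positive under one rule, negative under the other.
- At a 9-month median the chance of this is 0.817 − 0.586 = 0.231.
- On the normal approximation the critical 6-month survival is 0.5 + 0.0559z = 0.572 or 0.610. Under exponential survival these correspond to medians 6·ln2/(−ln 0.572) = 7.4 and 6·ln2/(−ln 0.610) = 8.4 months.

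**6. At the 12-month goal.** S(6) = 0.707, and the 6-month-survival test has 97.2% power at two-sided 5%. The Kaplan-Meier limit rules give 95.4% to 97.4%.

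**The case against.** The two-sided 5% sentence directly follows the one on exploratory comparisons, which contains every test the Analysis Plan names. It may well have been meant only for those. On that reading the specific statement in the sample size paragraph governs the primary endpoint, 80 patients and the stated power stand, and the fault is an omission rather than a contradiction. The size of the loss also depends on tests the protocol never proposes: a one-sample log-rank test keeps about 93% power, so the power claim would survive either level. The exact binomial falls short of 85% even at one-sided 10%, so it is probably not the design test. Finally, this is an exploratory single-arm phase II study that will report the median with a 95% interval, which any reader can set against 6.0 months.

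Much of this is fair. Neither the sample size nor the stated power is wrong in itself, the 95% intervals are not part of the conflict, and 58–67% should not be presented as the trial's power. But the sentence covers all p-values and exempts nothing. Even on the narrow reading, the Analysis Plan still lacks a primary test, level and success rule, so the power claim is attached to nothing. The log-rank figure does not rescue it: that test against an exponential reference relies on the distributional assumption that Section 8 keeps for planning only.

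**Conclusion.** The concern holds. Section 8 gives two incompatible significance levels for anything that would count as a primary test, and does not say which test that is or what result means success. Followed literally, the Analysis Plan does not deliver the stated power under the nonparametric tests of the median that reproduce it: about 86–87% becomes about 58–67%. Across all the tests considered, the range at two-sided 5% is about 58% to 93%.

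These figures assume a fixed 6.0-month reference, exponential survival, a true median of 9 months and, for the 6-month-survival tests, no censoring before 6 months. The 23% chance of a contradictory result belongs to the exact 6-month-survival test. The loss concerns the 9-month planning value; at a 12-month median, power is about 95% or more at either level.

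**What to change.** Two changes in Section 8, made before the OS data are analysed:

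1. State the primary rule at the design level and in nonparametric form. One option: *the primary analysis is positive if the lower one-sided 90% Kaplan-Meier confidence limit for median OS exceeds 6.0 months.*
2. Limit the two-sided 5% sentence to the hypothesis-generating comparisons between patient categories.

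If two-sided 5% is intended for the primary test, name the test and restate its power at a 9-month median: about 58–67% for a Kaplan-Meier-based rule, or about 93% for a one-sample log-rank test, with its reliance on an exponential reference made explicit.

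The cost is two sentences, with no new patients or data, and the 95% confidence intervals can stay. One drawback of the example rule is that its simulated type I error is about 11%, slightly above the nominal 10%.

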	
*Grade 3/4 in the CTCAE v4.0 grading would generally be considered clinically significant, although this remains a judgment for the Investigator to make.
 
 10. LVEF ≤ 50% 11. Baseline troponin I and b-type natriuretic peptide > Grade I 12. Prior exposure cardiotoxic agent, such as anthracycline within 3 months of enrollment 13. Concomitant use of drugs that prolong QT/QTc interval except antibiotics, antifungals, and other antimicrobials used as standard of care for the treatment and prevention of infection and/or other such drugs clinically indicated for patient care. When use of concomitant medications with QT-prolonging potential is necessary, ECG must be repeated 4 hours post-dose on Day 1 (+1 day), on Day 3 (±1 day), and on Day 7 (±1 day), and as clinically indicated, relative to start of agent with QT-prolonging potential. QTc will be calculated using the Fridericia formula. For subsequent use of same concomitant medication, ECG may not be repeated if it did not cause QTc prolongation with tosedostat. 14. Gastrointestinal disorders that may interfere with absorption of drug 15. Active serious infection or sepsis 16. Clinically significant interstitial lung disease
Study duration	24 months
Safety	Safety evaluations will include monitoring of adverse events (AEs); laboratory safety testing,

	including hematology and blood chemistry; urinalysis; physical examinations; vital signs; ECGs; and left ventricular ejection fraction (LVEF) determination. All reported symptoms and AEs will be coded using the Medical Dictionary for Regulatory Activities (MedDRA) and summarized. Crude incidence rates will be based on the maximum intensity grade for each subject. Descriptive statistics for other safety parameters will be produced. All subjects who receive any amount of tosedostat will be included in these analyses.
--	--

Table 1: LIST OF ABBREVIATIONS AND DEFINITIONS OF TERMS

AE	Adverse Event
ALT	Alanine Aminotransferase
AML	Acute Myeloid Leukemia
ANC	Absolute Neutrophil Count
APL	Acute Promyelocytic Leukemia
APTT	Activated Partial Thromboplastin Time
AST	Aspartate Aminotransferase
BP	Blood pressure
BSA	Body Surface Area
BUN	Blood Urea Nitrogen
CFR	Code of Federal Regulations
CFU/c	Colony-Forming Unit in Culture
CML	Chronic Myeloid Leukemia
CPK	Creatinine Phosphokinase
CR	Complete Remission
CPMP	CHMP - Committee for Medicinal Product for Human Use
CRm	Molecular Complete Remission

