2 STUDY OBJECTIVES

Primary Objective:

The primary objective of the study is to evaluate the safety and efficacy of tosedostat in patients with myelodysplastic syndrome who have relapsed after or are refractory or intolerant to azacitidine or decitabine. The primary endpoint for patients is overall survival.

Secondary Objectives:

The following secondary endpoints will be evaluated:

- Hematological improvements (erythroid response [ER], platelet response [PLR] and neutrophil response [NR]) according to 2006 IWG criteria (Appendix 3), including reduction in RBC and/or PLT transfusion needs
- Overall response (complete remission [CR], partial remission [PR], bone marrow complete response [BMCR], and stable disease [SD] according to 2006 International Working Group (IWG) criteria, including, among responders, the distribution of time to response and the duration of response. (Appendix 3)
- Improvements of cytogenetics as evaluated by the change in aneuploidy in BM according to 2006 IWG criteria
- Safety and tolerability of tosedostat
- Time to AML transformation

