3.2 DISCUSSION OF STUDY DESIGN

While the prognosis of MDS patients who are refractory to or have relapsed after treatment with hypomethylating agents is universally poor. For higher risk MDS patients, overall survival is extremely short, with estimates ranging from 3-6 months. Therefore, for this group, the primary endpoint is doubling of overall survival from 6 to12 months. The tosedostat dose of 120 mg per day for this study was chosen based safety, efficacy and convenience established in the prior studies CHR-2797-002 and OPAL. Based on preliminary clinical and in vitro data, it is possible that tosedostat may synergize with and/or restore sensitivity to the hypomethylating agent azacitidine. Therefore, for patients who have stable disease, but no hematological improvement after 2 cycles with tosedostat, the investigator may add azacitidine 75 mg/m² IV or SC for 5 days to tosedostat.

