5.7.4 Criteria for Protocol-Defined Required Discontinuation of Treatment

- Discontinue treatment with tosedostat if patients experience any of the following:
- Do not achieve CR, PR, hematologic improvement, or bone marrow remission after four cycles of treatment with tosedostat alone or 4 cycles of azacitidine if azacitidine is added to tosedostat.
- Experience disease progression
- Develop an intercurrent illness that prevents further treatment with tosedostat
- Develop unacceptable/intolerable AE(s)
- Withdraw from the clinical study
- Become pregnant
- Receive other systemic cancer therapy or protocol-prohibited medications
- Have general or specific changes that render the patient unsuitable for further treatment with tosedostat, in the judgment of the Investigator

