7.4.1 Safety Monitoring

This is an investigator-initiated trial. The Principal Investigator will be responsible for the study and will ensure that the protocol is being followed in accordance with current local IRB, FDA, and ICH regulations/guidelines.

In this research study, safety data is reviewed on a rolling basis. A formal safety interim analysis will take place after 40 patients have been enrolled and completed at least one cycle of treatment. The Investigator will review the following safety:

- Physical exam
- Vital signs
- Electrocardiogram (ECG)
- Left ventricular ejection fracture (LVEF)
- Laboratory parameters, includes blood counts, blood chemistries, urinalysis, coagulation, and cardiac panel
- Adverse events and serious adverse events

Based on the results of the interim analysis, the investigator may allow the study to proceed as is, modify the study, or terminate the study.

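### The safety tables do not separate tosedostat alone from tosedostat plus azacitidine; a descriptive split at the first azacitidine dose would cost little

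*Combined protocol and SAP*

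**What the plan says.** **Treatment.** Every patient starts on tosedostat alone. Section 6.3 then allows a second drug: "If at end of two cycles of tosedostat, patient does not have response as defined as above, the investigator has discretion of adding azacitidine". Section 3.2 describes the group more narrowly: "for patients who have stable disease, but no hematological improvement after 2 cycles with tosedostat, the investigator may add azacitidine". Section 5.7.4 stops treatment for non-response after four cycles of tosedostat alone or after "4 cycles of azacitidine if azacitidine is added to tosedostat".

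**Objective.** Section 2 puts the safety of tosedostat in the primary objective and lists "Safety and tolerability of tosedostat" again among the secondary endpoints.

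**Safety analysis.** The synopsis (Safety) gives the analysis set: "All subjects who receive any amount of tosedostat will be included in these analyses". It also gives the measure: "Crude incidence rates will be based on the maximum intensity grade for each subject". Section 8 (Adverse Events) gives the layout, "They will be tabulated by SOC and by preferred term within SOC according to MedDRA", with exact 95% confidence intervals around the proportions.

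**Monitoring.** Section 7.4.1 states: "A formal safety interim analysis will take place after 40 patients have been enrolled and completed at least one cycle of treatment". Section 7.4.4 adds an early DSMB review, semiannual reviews, review of all serious adverse events, and a threshold of 8 or more drug-related grade V events. None of these is described by regimen.

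**The concern.** A reader of the final tables will take them as the safety profile of tosedostat, because that is the objective they answer. Under the stated rules they describe tosedostat with or without azacitidine, in a mix set by investigators' choices.

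Two things follow. An event that first occurs on the combination is counted in the tosedostat incidence. And an event seen on tosedostat alone that recurs at a higher grade on the combination appears once, at the higher grade, with nothing to show that the grade arose after a second drug was added.

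The gain from a split lies mainly in common and lower-grade toxicity and in the final report, since deaths and other serious events reach the DSMB individually. The earlier combination study cited in section 1.1.4.4 does not supply the missing information: it enrolled 10 subjects and gave azacitidine for 7 days per cycle, against 5 days here (section 6.3).

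**Working it through.** The plan states no figure on this point, so there is nothing to reproduce. The check has three parts.

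**1. Is there a split anywhere in the documents?**

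- Section 8 does plan comparisons by treatment characteristics, but for transfusion independence and overall survival, not for adverse events.
- Section 7.3.6.2 asks for one causality judgement, related or unrelated to the study medication. It has no separate attribution to azacitidine.
- Section 7.3.6.4 mentions azacitidine labelling only for judging whether a single event is expected.
- Sections 7.4.1 and 7.4.4 specify no presentation by regimen.

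No split is specified.

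**2. Does the single incidence depend on uptake?** Let *a* be the risk of a given event on tosedostat alone, *b* the risk after azacitidine among those still event-free, and *f* the proportion who add azacitidine. The per-subject incidence is

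P = 1 − [(1 − a)(1 − f) + (1 − a)(1 − b)f] = a + (1 − a)·b·f.

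The documents give none of these inputs, so all values below are assumptions.

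| f | a = 20%, b = 40% | a = 20%, b = 20% |
|---|---|---|
| 20% | 0.20 + 0.80 × 0.40 × 0.20 = 26.4% | 0.20 + 0.80 × 0.20 × 0.20 = 23.2% |
| 40% | 32.8% | 26.4% |
| 60% | 39.2% | 29.6% |

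The middle column shows the same two drugs giving different reported incidences only because uptake differs. The right-hand column shows that incidence rises with uptake even when the risk is the same in both periods, because those who add azacitidine are observed for longer. Crude percentages by period are therefore not enough; time at risk must be shown.

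**3. What precision would a split have?** All 80 patients contribute to the first period. The second-period size is unknown; 16 and 40 are assumed here (20% and 50% of 80). Exact (Clopper-Pearson) 95% intervals at an observed rate of 25%:

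- first period, 20/80: 16.0% to 35.9%
- second period, 10/40: 12.7% to 41.2%
- second period, 4/16: 7.3% to 52.4%

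These intervals are wide enough that the split can describe but not test.

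**Data already collected.** Section 7.3.6.3 asks for onset and resolution dates and severity of each event. Section 6.6 asks for dates of use of medications. Section 7.4 says that all treatment and toxicity data go into REDCap. Two gaps remain. The schedule in Appendix 1 has no azacitidine row, so the first-dose date is implied rather than an explicit field. And section 7.3.6.3 names no date for a change in grade.

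**The case against.** The strongest reply is that the protocol is silent rather than restrictive. The section 8 sentence gives a coding hierarchy, not table columns, and the list of safety outputs there is not closed. The data and safety monitoring plan mentioned in section 7.4.4 is not among the documents and may contain a split. An all-patient table is also a legitimate summary of the strategy under test, which is tosedostat with optional azacitidine. All of this stands. It is why the point is that the outputs *do not separate* the regimens, and why the all-patient tables should stay. It does not remove the gap: the stated measure, applied as written, yields a figure that cannot be read as tosedostat alone.

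A reader might go further and infer that patients on the combination are inadequately monitored. The documents do not support that. Rolling review, the 40-patient interim, semiannual DSMB meetings, review of all serious events, the grade V threshold and DSMB access to the database (section 7.4) all include these patients.

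A reader might also want to say by how much combination toxicity would be masked, or what share of treatment time would be on the combination. The documents do not allow it. Uptake is discretionary and not stated. The eligible group is not sharply defined: section 3.2 requires stable disease without hematological improvement, while section 5.2.2 lists stable disease among documented responses. The permitted duration is also unclear, since section 4.3 allows up to four cycles to achieve a response and section 5.7.4 allows four cycles with azacitidine.

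**Conclusion.** The concern holds as a reporting improvement of low priority. The planned safety analysis does not separate tosedostat alone from tosedostat plus azacitidine, so the incidence reported for the objective depends on an unstated uptake. In the illustration it runs from 26.4% to 39.2% with the underlying risks unchanged. That range rests wholly on assumed risks and uptake; it shows the dependence and does not forecast its size.

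The sample size, type I error and survival power are untouched.

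A split would not identify an azacitidine effect, although a reader might take a difference between periods as one. The second period contains only surviving non-responders whom the investigator chose to treat, later in their disease and with different exposure time.

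**What to change.** In section 8, and in the summaries for the 40-patient interim (7.4.1) and the DSMB (7.4.4), keep the all-patient tables and add one descriptive layout:

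- Assign each adverse event by onset date to the period before the first azacitidine dose or the period from that dose onward. Patients who never receive azacitidine contribute only to the first period.
- Count an event that begins before azacitidine and worsens in grade afterwards in the second period as well, at its worse grade.
- Show the patients at risk and the patient-months (or cycles) in each period.
- Record the first and last azacitidine dose dates as explicit eCRF fields. The last date shows how much of the second period was spent on both drugs.
- State that the comparison is descriptive, because of the selection and exposure differences between the periods.

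**Cost.** Protocol wording, one extra table layout, two date fields, and a date of worsening for events that change grade across the boundary. No additional patients, visits, procedures, DSMB meetings or type I error are needed. The downside is sparse second-period tables with wide intervals, which could be over-read if the caveat is left out.
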